16.1.1 Table 17.2.1

Consequences for Outcomes and Their Precision of Having a Randomized Pilot Study with Specified Parameters.

States of Nature	Parameters				Outcomes (Percentiles)				
	Limits			20%	80%				
rate	80%T	n	t	s	n	t	p(init)	p(ret)	$ \hat{T} - T $
							(95% CI Half width)		
n-limited									
1.14	46	50	.	1	50	49	0.2	0.21	5
1.14	46	50	.	2	50	25	0.2	0.21	5
2.28	23	50	.	1	50	25	0.2	0.21	3
2.28	23	50	.	2	50	12	0.2	0.21	3
t-limited									
1.14	46	.	12	1	9	12	0.45	0.47	12
1.14	46	.	12	2	22	12	0.3	0.32	8
2.28	23	.	12	1	22	12	0.3	0.32	4
2.28	23	.	12	2	48	12	0.21	0.22	3
1.14	46	.	18	1	16	18	0.37	0.38	9
1.14	46	.	18	2	35	18	0.24	0.25	6
2.28	23	.	18	1	34	18	0.24	0.26	3
2.28	23	.	18	2	73	18	0.17	0.17	2
both n- and t-limited									
1.14	46	50	12	1	10	12	0.47	0.5	12
1.14	46	50	12	2	22	12	0.3	0.32	8
2.28	23	50	12	1	22	12	0.3	0.32	4
2.28	23	50	12	2	48	12	0.21	0.22	3
1.14	46	50	18	1	16	18	0.35	0.37	9
1.14	46	50	18	2	35	18	0.24	0.25	6
2.28	23	50	18	1	34	18	0.24	0.25	3
2.28	23	50	18	2	50	12	0.2	0.21	3

To use **Table 17.2.1**, observe that the columns are broken into three groups:

States of Nature: These are design quantities that are fixed by nature. That is, you have to assume them, but you cannot manipulate them to get a better pilot study. These include the recruitment rate and its implication for the 80th percentile of the time it will take to recruit in the phase III randomized trial.

Parameters: These are design quantities that you can choose to optimize the pilot study. They include the limits on pilot-study sample size (n) and time to recruit (t), and the number of sites (s) in the pilot study.

Outcomes: These are the results of the States of Nature assumed and the Parameters chosen. They include the 20th percentile of the pilot study sample size and the 80th percentiles of t, p(init), p(ret) and $|\hat{T} - T|$.

For example, the highlighted row in the last – “paragraph” of **Table 17.2.1** shows that, if you assume that the pilot study recruitment rate is 2.28 participants per site-month (implying that the phase III randomized trial will likely require no more than 23 months to recruit), and if you choose to stop the pilot study after either 50 participants or 12 months of enrollment time (whichever comes first), and you choose to have two sites in the pilot study, then it is likely that the pilot study will recruit at least 48 participants and stop recruitment at 12 months. In this case, the 95% confidence intervals for $p(\text{init})$ and $p(\text{ret})$ will very likely be no wider than ± 0.22 and the prediction derived from the pilot study of the recruitment time for the subsequent randomized study will probably be off by no more than ± 3 months. This degree of imprecision appears acceptable for the pilot study.

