The proposal for a phase III randomized trial assumes enrollment of 400 participants from 8 sites in 18 months, implying a recruitment rate of about 2.28 participants per site-month. **Table 17.2.1** explores by simulation the consequences for the precision of various pilot-study-derived estimates of having a pilot study in which per site-month recruitment rate = (1.14, 2.28), number of sites = (1,2), and time period = (12 months, 18 months). **Table 17.2.1** investigates limiting the pilot sample size to 50 participants (n-limited), or limiting the enrollment time to 12 or 18 months (t-limited), or limiting both sample size and recruitment time simultaneously (n- and t-limited). The columns of **Table 17.2.1** headed – “Parameters” depict all the parameter combinations investigated.

5) The notation used in **Table 17.2.1** follows:

- n = pilot study sample size
- t = pilot study recruitment time (months)
- s = number of sites in the pilot study
- rate = recruitment rate (participants per site-month) assumed for both the pilot study and the subsequent phase III randomized trial
- N = randomized trial sample size (assumed to be 400)
- T = randomized trial recruitment time (months). This assumes that the sites in the randomized trial will exhibit the same performance that they did in the pilot study.
- S = number of sites in the randomized trial (this is not actually shown in **Table 17.2.1**, but is assumed to be 8)
- $\hat{T} = \frac{s/n}{S/N} t$, the estimator, derived from the pilot study, of the recruitment time for the subsequent phase III randomized trial
- $p(\text{init})$ = the probability of treatment initiation, which is the chance that a participant who is randomized to one of the two arms within the pilot study will obtain the 1st dose of the treatment. There is one $p(\text{init})$ calculated for each of the two arms.
- $p(\text{ret})$ = the probability of retention, which is the chance that a pilot-study participant who has obtained the 1st dose will still be on treatment at 4 months. There is one $p(\text{ret})$ calculated for each of the two arms.

6) The columns of **Table 17.2.1** headed “Outcomes (Percentiles)” show the consequences for various outcomes, given the parameters controlling the pilot study. Their meanings follow:

- 20% n = the 20th percentile of the sample size of the pilot study. The pilot study will very likely recruit at least this many participants

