- 80% t = the 80th percentile of the recruitment time for the pilot study (months). The pilot study will very likely not take longer than this time to recruit.
- 80% $p(\text{init})$ = the 80th percentile of the 95% confidence interval half width for the pilot- study-derived estimate of the probability of treatment initiation. If this value is x , it means that the 95% confidence interval for the estimate of the probability of treatment initiation will very likely not be wider than $\pm x$.
- 80% $p(\text{ret})$ = the 80th percentile of the 95% confidence interval half width for the pilot- study-derived estimate of the probability of treatment retention. If this value is x , it means that the 95% confidence interval for the estimate of the probability of treatment retention will very likely not be wider than $\pm x$. This confidence interval is slightly wider than for $p(\text{init})$ because **Table 17.2.1** assumes 10% attrition between the time of recruitment and initiation.
- 80% T = the 80th percentile of the time to recruit in the subsequent phase III randomized trial.
- 80% $|\hat{T} - T|$ = the 80th percentile of the absolute value of the predictive bias of \hat{T} for T

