17.3 Analysis of Randomized Pilot Study Primary Outcomes

The probability of treatment initiation (Aim 4A) and the probability of retention on treatment (Aim 4B), which are calculated separately for the two arms, are both based on ordinary (conditional) binomial samples, and will be estimated using maximum likelihood techniques, with exact binomial confidence intervals. We do not contemplate a multiplicity adjustment.

The rate of participant recruitment into the trial (Aim 3) can be estimated simply using maximum likelihood assuming an underlying Poisson process, but we feel it is more meaningful and useful for planning to predict the time required for recruitment in a subsequent randomized trial with 400 participants coming from 8 sites. We will do this via a bootstrap simulation. In each iteration of the simulation, the steps will be as follows:

- Draw a bootstrap sample of 8 sites from the 2 pilot-study sites.
- For each site, draw a bootstrap sample of, say, 1000 inter-arrival times from the inter-arrival times for that site to get 1000 simulated enrollment times (starting from time 0) for the site. Note that we consider that the time between the last enrollment at that site and the 12 month time point is also an inter-arrival time for that site. We will use this inter-arrival time in the simulation, but will not associate it with a simulated enrollment¹.
- Treating the 8 bootstrapped sites as simultaneously enrolling, determine T, the time of enrollment of the 400th patient in the simulated trial.

Repeating this iteration 10,000 times will generate 10,000 T-values that will constitute a predictive distribution for the enrollment times in the subsequent randomized trial. It is necessary to assume that the sites in the pilot study are a representative sample of the sites that will participate in the subsequent randomized trial.

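### The error column of Table 17.2.1 is too small for the percentile it claims (about 4.4 months, not 3, in the design row), and the section 17.3 bootstrap omits most of the pilot's own sampling error

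*Protocol*

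**What the plan says.** Section 17.2 of the protocol estimates the phase III recruitment time T from the pilot as T-hat = [(s/n)/(S/N)] × t, where s, n and t are the pilot's sites, participants and months. For phase III it takes S = 8 sites and "N = randomized trial sample size (assumed to be 400"). The last column of Table 17.2.1 is defined as "the 80th percentile of the absolute value of the predictive bias of" T-hat for T.

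The worked example below the table reads the design row: "if you assume that the pilot study recruitment rate is 2.28 participants per site-month", with recruitment closing at 50 participants or at month 12, and with two sites. The tabulated error is 3 months, and the text concludes that "the prediction derived from the pilot study of the recruitment time for the subsequent randomized study will probably be off by no more than" that figure in either direction. It then calls this degree of imprecision acceptable for the pilot.

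Section 17.3 fixes the Aim 3 analysis step by step. Each iteration begins: "Draw a bootstrap sample of 8 sites from the 2 pilot-study sites". It then resamples inter-arrival times from those observed at each drawn site and finds the time of the 400th enrollment. The wait from a site's last enrollment to month 12 is kept as an interval that does not end in an enrollment. "Repeating this iteration 10,000 times will generate 10,000 T-values that will constitute a predictive distribution for the enrollment times in the subsequent randomized trial".

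**The concern.** The tabulated errors look too small for the sampling variation of a pilot with about 50 arrivals. In the first row of the table, the stated 80% bound is smaller than one standard deviation of the estimator alone.

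The bootstrap raises a related problem. A predictive distribution for T should carry two sources of uncertainty: the chance variation of the phase III trial itself, and the pilot's uncertainty about the recruitment rate. Resampling 400 arrivals from a fixed set of about 25 intervals per site carries the first and little of the second.

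Aim 3 is a primary outcome, and its declared purpose is to predict the length of a later trial. If the planning figure and the eventual predictive range are both too narrow, the later trial will be planned with more confidence than the pilot can give.

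**Working it through.** **Inputs.** Rate 2.28 or 1.14 per site-month, N = 400, S = 8, the estimator and the row limits, all from section 17.2. Assumption: Poisson arrivals. The protocol does not state the model behind the table; Poisson is the only arrival model it names (section 17.3, for the Aim 3 rate).

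**Reproducing the design row** (2.28; 50 participants or 12 months; 2 sites) by simulation:

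| Quantity | Stated | Simulated |
|---|---|---|
| 20th percentile of n | 48 | 48 |
| 80th percentile of t | 12 | 12 |
| 80th percentile of T | 23 | 22.9 |
| 80th percentile of the absolute error | 3 | 4.4 |

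The model therefore fits the recruitment columns, and the error column is the one that fails.

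**Hand check, design row.**
- Mean T = 400/(8 × 2.28) = 21.93 months; SD(T) = √400/18.24 = 1.10.
- SD(T-hat) ≈ 21.93/√50 = 3.10, taking n = 50.
- SD of the error ≈ √(3.10² + 1.10²) = 3.29.
- 80% absolute bound ≈ 1.2816 × 3.29 = 4.2 months.

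The simulated 4.4 is slightly larger because some pilots reach month 12 with fewer than 50 participants. The simulated probability of an error of 3 months or less is 0.62.

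**Hand check, first row** (1.14; 50 participants; 1 site).
- T-hat = [(1/50)/(8/400)] × t = t, so it equals the pilot's duration.
- SD(T-hat) = √50/1.14 = 6.2; SD(T) = √400/9.12 = 2.2; combined √(6.2² + 2.2²) = 6.6.
- 80% bound ≈ 1.2816 × 6.6 = 8.4, against 5 stated.

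**Other rows.** With 1.14 per site-month and a 12-month limit alone, the percentile is 11.2 for two sites (stated 8) and 15.8 for one site (stated 12). In none of the 20 rows does the simulated percentile round to the stated value; the ratio runs from 1.31 to 1.72. Variants of the estimator (n − 1, n + 1, time of last arrival) and counting pilot participants towards the 400 do not rescue the column either.

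**Bootstrap.** The section 17.3 procedure was coded and repeated over 3,000 simulated pilots with 300 bootstrap draws each, at 2.28 with identical sites:

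| Final gap ends | Half-width of central 95% | Bootstrap SD | Coverage of true T |
|---|---|---|---|
| when the pilot stops | 2.9 months | 1.5 | 58% |
| always at month 12 | 3.6 months | 1.8 | 69% |

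The actual prediction error has an SD of about 3.3 months. The bootstrap SD of 1.5 consists of phase III noise (1.1) plus what the draw of 8 sites from 2 adds.

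The 69% under the literal month-12 reading is not a sign of better calibration. A pilot that reaches 50 early is then treated as if it had taken 12 months, so its prediction sits near (2/50)/(8/400) × 12 = 24.0 however fast it recruited. The simulated median prediction is 24.0, against a true mean of 21.9.

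Drawing each site's rate from its sampling uncertainty first, with the gap ending at actual closure, gives about 96% coverage and a range of about 14 months.

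**The case against.** **The sentence is loose.** The worked example says only that the prediction will probably be within 3 months, while it uses stronger language for the confidence intervals. At 62%, that sentence is literally true. This stands. What is wrong is the column's label as an 80th percentile, and the judgement of acceptability that draws on the figure.

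**No interval is promised.** A reader might infer that the protocol will report a 95% interval that misses the truth about 40% of the time. The documents do not support that. Section 17.3 names no level and no interval, and its summary may be left to the analysis plan. The figure of about 40% also fits only the reading in which the gap ends at pilot closure; the literal month-12 reading misses about 31%. The coverage figures here describe the central 95% of what the protocol calls a predictive distribution.

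**The cause is unknown.** A reader might infer that a signed 80th percentile was tabulated by mistake. After rounding, that matches only 10 of 20 rows, whereas the mean absolute error matches 16 of 20. Neither explanation is established, and the point does not need one.

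**Representative sites are assumed.** Section 17.3 does state this assumption. It does not help, because the shortfall appears with identical sites. Coverage under a chosen between-site spread would rest on an input that the protocol does not give, so the conclusion does not use it.

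**The consequence is limited.** The protocol sets no go/no-go threshold on predicted recruitment time, the pilot is capped whatever the result, and no participant-level analysis changes. This stands and limits the weight of the point.

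**Conclusion.** Both parts hold. Under Poisson arrivals, the last column of Table 17.2.1 is not the percentile that section 17.2 defines: the design row should read about 4.4 months instead of 3, and 3 months is about a 62% bound. The bootstrap in section 17.3 leaves out most of the pilot's sampling error, so at 2.28 with identical sites the central 95% of its output covers the true recruitment time in about 58% to 69% of pilots.

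The size depends on the Poisson assumption, on the rate of 2.28, on identical sites, and on how the final gap is read. The point should be corrected because the protocol itself prints the figure and prescribes the algorithm. It does not threaten participants or the arm comparisons.

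**What to change.** - **Section 17.2.** Recompute the last column of Table 17.2.1 as the 80th percentile of the absolute error and state the arrival model used. Change the worked example to about 4.4 months, and judge afresh on that figure whether the imprecision is acceptable.
- **Section 17.3.** Add a first stage to each iteration that draws each pilot site's rate from its sampling uncertainty, for example a Gamma draw based on the number enrolled and the site-months open, or a resample of that site's pilot intervals. End the final gap when the pilot actually closes.
- **Optional.** Show the prediction under a few assumed between-site coefficients of variation, labelled as assumptions, since two sites can hardly estimate that spread.

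The cost is a few lines of simulation code and some text. The stated precision becomes less favourable, and the central 95% range widens to about 14 months from about 6 to 7 (2 × 2.9 = 5.8 and 2 × 3.6 = 7.2). No design, visit or clinical procedure changes.

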17.3 Analysis of Randomized Pilot Study Primary Outcomes

The probability of treatment initiation (Aim 4A) and the probability of retention on treatment (Aim 4B), which are calculated separately for the two arms, are both based on ordinary (conditional) binomial samples, and will be estimated using maximum likelihood techniques, with exact binomial confidence intervals. We do not contemplate a multiplicity adjustment.

The rate of participant recruitment into the trial (Aim 3) can be estimated simply using maximum likelihood assuming an underlying Poisson process, but we feel it is more meaningful and useful for planning to predict the time required for recruitment in a subsequent randomized trial with 400 participants coming from 8 sites. We will do this via a bootstrap simulation. In each iteration of the simulation, the steps will be as follows:

- Draw a bootstrap sample of 8 sites from the 2 pilot-study sites.
- For each site, draw a bootstrap sample of, say, 1000 inter-arrival times from the inter-arrival times for that site to get 1000 simulated enrollment times (starting from time 0) for the site. Note that we consider that the time between the last enrollment at that site and the 12 month time point is also an inter-arrival time for that site. We will use this inter-arrival time in the simulation, but will not associate it with a simulated enrollment¹.
- Treating the 8 bootstrapped sites as simultaneously enrolling, determine T, the time of enrollment of the 400th patient in the simulated trial.

Repeating this iteration 10,000 times will generate 10,000 T-values that will constitute a predictive distribution for the enrollment times in the subsequent randomized trial. It is necessary to assume that the sites in the pilot study are a representative sample of the sites that will participate in the subsequent randomized trial.

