Aim 4: Assess the feasibility of integrating XR-NTX for opioid and alcohol use disorders into HIV clinics. Data collection during study start-up will inform selection of 2 HIV clinics to implement XR-NTX treatment. HIV providers and staff will be trained in detoxification and XR-NTX induction and management. HIV-infected subjects with untreated opioid and/or alcohol use disorders will be randomized to XR-NTX or TAU, followed by detoxification (if needed) and treatment induction. The primary outcomes are 1) treatment initiation (successful treatment initiation of XR-NTX or TAU within 4 weeks of randomization), and 2) retention on treatment condition at 16 weeks. Secondary outcomes include change in 1) HIV-1 RNA viral suppression, 2) Illicit drug and alcohol use, 3) HIV care engagement (receipt of ART, HIV visit adherence, ART adherence), and safety (percent with precipitated withdrawal, hepatotoxicity, or overdose).

Aim 4 Pilot Objective A: Estimate effect size point estimates for rate of treatment initiation and 16 week retention among HIV-infected patients with alcohol or opioid use disorders randomized to XR-NTX vs. TAU.

Aim 4 Pilot Objective B: Estimate effect size point estimates for secondary outcomes of HIV-1 RNA viral suppression, illicit drug and alcohol use, HIV care engagement, and safety among HIV-infected patients with alcohol or opioid use disorders randomized to XR-NTX vs. TAU.

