5.0 OBJECTIVES

5.1 Primary Objectives

The overarching goal of the CHOICES pilot study is to determine the acceptability and feasibility of XR-NTX in HIV practice and inform development of a multi-site comparative effectiveness trial of XR-NTX vs. TAU in HIV clinics. We will achieve this goal by pursuing four primary pilot study objectives. Specific measures of study objectives outcomes are defined in Section 8.0.

- Objective #1:** Assess HIV provider acceptability of antagonist therapy by estimating the proportion of HIV providers willing to prescribe XR-NTX for opioid and/or alcohol use disorders.
- Objective #2:** Assess HIV-infected patient acceptability of antagonist therapy by estimating the proportion of potential subjects approached willing to take XR-NTX and be randomized to a trial of XR-NTX vs. TAU.
- Objective #3:** Estimate the rate of participant recruitment into a future comparative effectiveness trial based on this pilot study.
- Objective #4A:** Compare successful treatment initiation within 4 weeks of randomization in participants randomized to receive XR-NTX vs. TAU for opioid and alcohol use disorders in HIV clinics.
- Objective #4B:** Compare treatment retention at 16 weeks following treatment initiation in participants randomized to receive XR-NTX vs. TAU for opioid and alcohol use disorders in HIV clinics.

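### Objectives 4A and 4B call for an XR-NTX versus TAU comparison, but section 17.3 plans only separate arm-specific estimates, with no between-arm effect measure or interval

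*Protocol*

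**What the plan says.** - **Objectives (5.1).** Objective 4A is to "Compare successful treatment initiation within 4 weeks of randomization in participants randomized to receive XR-NTX vs. TAU". Objective 4B is to "Compare treatment retention at 16 weeks following treatment initiation in participants randomized to receive XR-NTX vs. TAU".
- **Aim 4 Pilot Objective A (2.1).** "Estimate effect size point estimates for rate of treatment initiation and 16 week retention among HIV-infected patients", again for XR-NTX vs. TAU.
- **Analysis (17.3).** The probabilities of initiation and retention, "which are calculated separately for the two arms", "will be estimated using maximum likelihood techniques, with exact binomial confidence intervals". No multiplicity adjustment is planned. No between-arm quantity is named here, or in 17.6 to 17.8 for these outcomes.
- **Precision (17.2, Table 17.2.1 and the worked example after it).** The notation says that one p(init) and one p(ret) are calculated for each arm. For two sites, a limit of 50 participants or 12 months and 2.28 participants per site-month, the table gives half-widths of 0.21 and 0.22. The example concludes that the 95% intervals "will very likely be no wider than" ±0.22 and that this is acceptable for the pilot.
- **Secondary outcomes (17.5).** Several do get a between-arm analysis, for example a chi-squared test of viral suppression against treatment assignment.

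**The concern.** The stated objective and the planned analysis are different quantities. The objective is a contrast between randomized arms; the analysis is two one-sample estimates. Section 17.3 does not leave this open for later detail: it fixes the target, the estimator, the interval type and the multiplicity position, and none of these yields an effect measure with its uncertainty. Several secondary outcomes have a planned contrast while the two randomized primary outcomes have none.

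Two things are at stake. First, readers given two separate intervals tend to judge the comparison by whether they overlap, which is not a valid reading of a difference. Second, the precision discussed in 17.2 belongs to the arm-specific proportions. The precision of the comparison named in 4A and 4B is not stated, so its adequacy has not been considered in the protocol.

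**Working it through.** **Inputs.** Likely sample size of at least 48 (worked example after Table 17.2.1) with 1:1 allocation (6.1): 24 per arm. Ten percent attrition before initiation (17.2): 24 × 0.9 = 21.6, about 22 per arm for retention. Confidence level 95%. The protocol gives no expected rates by arm, so p = 0.5 is used as the worst case and other values are shown as assumptions.

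**Step 1: reproduce the plan's figures.** Exact (Clopper-Pearson) 95% interval for one arm at p = 0.5:
- 12/24: 0.291 to 0.709, half-width 0.209 (table: 0.21)
- 11/22: 0.282 to 0.718, half-width 0.218 (table: 0.22)

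The stated figures are therefore single-arm half-widths, and they are right as such.

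**Step 2: half-width of the difference.** Wald: 1.96 × √(p₁q₁/n₁ + p₂q₂/n₂). Newcombe: the two Wilson intervals combined by square-and-add.

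| Outcome | n per arm | Rates assumed | Newcombe | Wald |
|---|---|---|---|---|
| Initiation | 24 | 0.5, 0.5 | 0.263 | 1.96 × √(0.5/24) = 0.283 |
| Initiation | 24 | 0.8, 0.6 | – | 0.253 |
| Initiation | 24 | 0.9, 0.9 | – | 1.96 × √(0.18/24) = 0.170 |
| Retention, if binary | 22 | 0.5, 0.5 | 0.273 | 0.295 |
| Retention, if binary | 22 | 0.9, 0.9 | – | 0.177 |

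With 21.6 rather than 22 per arm, the worst-case Wald figure for retention is 0.298.

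**Step 3: compare like outcome with like at p = 0.5.** Initiation: 0.263/0.209 = 1.26 and 0.283/0.209 = 1.35. Retention: 0.273/0.218 = 1.25 and 0.295/0.218 = 1.35. With unrounded half-widths the range over both outcomes is about 25% to 36% wider than the per-arm figure.

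**Step 4: why two intervals are not the comparison.** Illustration with assumed counts: 16/24 against 8/24. The exact intervals are 0.45 to 0.84 and 0.16 to 0.55, which overlap. The difference is 0.33 with Newcombe 95% interval 0.05 to 0.55, which excludes zero.

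**Step 5: is retention ready for a contrast?** Sections 8.1 and 17.1 define retention as the mean percent of assigned treatment received, among initiators only. Section 17.2 defines p(ret) as the chance that someone who obtained the first dose is still on treatment at 4 months, and 17.3 analyses a binomial probability. A mean percent calls for a difference in means, a binary status for a difference in proportions. Either way, the denominator is restricted to initiators, who are selected after randomization.

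**The case against.** **The effect size can be had by subtraction.** This stands. Pilot Objective A asks for point estimates, 17.3 yields a proportion in each arm, and 17.6 fixes analysis by assigned arm. A reader might infer that the effect size will never be produced; that is too strong. What the protocol lacks is a named effect measure and its interval. A statistical analysis plan, not shown here, may add them.

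**The ±0.22 is not an error.** This also stands. A reader might infer that the protocol presents it as the precision of the comparison. It does not: 17.2 says explicitly that the quantities are per arm, and judging a feasibility pilot on per-arm precision is defensible.

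**The follow-on trial may not need this contrast.** This partly stands. Section 6.3 describes a multisite trial with viral suppression as its primary outcome, and 17.2 already assumes 400 participants, so the protocol does not say that the initiation or retention contrast will size it. But the objectives ask for the comparison whatever its later use.

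**The size of the loss is a worst case, and interval methods are mixed.** The first part stands: the attrition assumption implies initiation near 0.9, where the Wald half-width of the difference is about 0.17. Mixing methods does not inflate the ratio: Wald against Wald at 24 per arm is 0.283/0.200 = 1.41. The comparison in the working is with the exact interval because that is the one the protocol plans.

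**The pilot is too small to test.** The remark in 17.5 that the study is probably under-powered concerns hypothesis tests. It is no argument against an estimate with an interval.

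**Conclusion.** The mismatch holds on the protocol's own text. Sections 2.1 and 5.1 ask for a comparison and effect sizes; 17.3 plans separate arm estimates, and no between-arm measure or interval is planned for the two randomized primary outcomes.

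For initiation, which is binary and defined in everyone randomized, the difference would have a half-width of about 0.26 to 0.28 at worst and about 0.17 if both arms are near 0.9, assuming 24 per arm. For retention, 0.27 to 0.30 at worst with about 22 per arm applies only if the endpoint is treated as binary, and the contrast is not a full randomized comparison.

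The word compare might also be read as requiring a hypothesis test. The documents do not require one, and with 24 per arm a two-sided 5% test would need a difference of about 0.37 to 0.40 for 80% power (lower rate assumed 0.5 or 0.3). Estimation with an interval is the suitable form.

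**What to change.** 1. **4A, in 17.3.** Add the difference in initiation proportions, XR-NTX minus TAU, in all randomized participants, with a 95% Newcombe or Miettinen-Nurminen interval. Keep the arm-specific exact intervals.
2. **4B, in 8.1, 17.1, 17.2 and 17.3.** First settle whether retention is a mean percent or a binary status. Then add the matching between-arm difference with a 95% interval, labelled as a comparison among initiators.
3. **Precision, beside Table 17.2.1.** Leave the per-arm figures as they are and add the half-width of the difference: for initiation, about 0.26 to 0.28 at p = 0.5 and about 0.17 (Wald) near 0.9; for retention, 0.27 to 0.30 at p = 0.5 if it is binary.

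If only arm-specific estimation is intended, the alternative is to reword Objectives 4A and 4B and Aim 4 Pilot Objective A to say so.

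The cost is wording, two further lines of analysis and a less favourable precision figure. No new data, participants or visits are needed.
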